### 10.2. SECONDARY EFFICACY ANALYSIS

The secondary efficacy analysis will be performed on the following measures.

All the secondary efficacy analyses will be performed using the ITT population and also for data exploration using the safety population.

## 10.2.1. The percentage of patients who reach the initial pre-specified target SBP range without falling below the lower limit of the pre-specified target range during the first 30 minutes of clevidipine infusion

The percentage of patients reaching this endpoint will be calculated using the number of patients reaching the endpoint divided by total number of patients in the analysis population, and multiplied by 100. Two-tailed 95% CIs will be computed for these percentages.

Number and percent of patients achieving the endpoint during first 30 minutes of clevidipine infusion along with the calculated 95% CI will be presented.

# 10.2.2. The percentage of patients in whom the SBP falls below the lower limit of the pre-specified target range at any time during the first 30 minutes of treatment and at any time during the entire study drug treatment period

Two analyses will be presented: the percentage of patients in whom the SBP falls below the lower limit of the pre-specified target range at any time during the first 30 minutes of treatment period and below the lower limit of the target range at any time during the entire study drug treatment period. Both endpoints will be calculated using the number of patients achieving the endpoint divided by total number of patients in the analysis population, and multiplied by 100. Two-tailed 95% CIs will be computed for these percentages.

Number and percent of patients achieving the endpoints along with the calculated 95% CI will be presented.

### 10.2.3. The percentage of patients in whom the SBP is within target range at each hour after the first 30 minutes of clevidipine infusion

The percentage of patients who stayed within target range at each hour after first 30 minutes of clevidipine infusion will be calculated using the number of patients who reached the endpoint divided by total number of patients in the analysis population, and multiplied by 100. Two-tailed 95% CIs will be computed for these percentages.

Time windows specified in Section 20.1.1 will be applied if the hemodynamic assessment is missing at a specific timepoint.

Number and percent of patients achieving the endpoint at each hour after first 30 minutes of clevidipine infusion along with the calculated 95% CI will be presented.

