If the desired BP control effect is not attained using the maximum dose of clevidipine, rescue therapy with the use of an alternative IV antihypertensive agent should be implemented. Patients who receive rescue therapy along with clevidipine may continue in the study. The alternative agent should be chosen per the institutional practice. The use of an alternative IV antihypertensive agent is discouraged and should be limited to situations where it is medically necessary to maintain patient safety as determined by the principal investigator.

If an additional/alternative IV antihypertensive agent is required, the clevidipine infusion may be down-titrated or terminated after initiation of the antihypertensive infusion in order to achieve the desired blood pressure level. If a patient is receiving rescue therapy with an IV antihypertensive treatment *and* transition to an oral antihypertensive agent is required, institutional practice must be followed. An alternative/additional IV antihypertensive agent that is administered as 'rescue therapy' will be recorded as rescue therapy in the eCRF. The following assessments will be performed during the titration and maintenance phase:

>1.5 Minutes – 30 Minutes Post Study Drug Initiation

- PK Sample 3: obtain 1.5 minutes after the first dose titration of study drug (taken in the order below)
 - BP and HR
 - PK Sample 3 (Table 1), taken immediately following BP and HR measurements
- Then, every 1.5 minutes for the remaining first 30 minutes post-study drug initiation:
 - BP and HR
- PK Sample 4: obtain once target range is achieved, or at 30 minutes if target range is not achieved (taken in the order below):
 - BP and HR
 - PK Sample 4 (Table 1), taken immediately following BP and HR measurements
 - BP and HR, taken every 1.5 minutes for the remaining first 30 minutes poststudy drug initiation, as instructed above.

- PK Sample 5: only taken if transition to an additional antihypertensive is desired and concurrent administration is needed prior to the end of the first 30 minutes (taken in the order below)
 - BP and HR
 - PK Sample 5 (as applicable): taken immediately after BP and HR and before beginning administration of an additional antihypertensive agent
 - BP and HR, taken every 1.5 minutes, as instructed above, for the remaining first 30 minutes post-study drug initiation if the PK Sample 5 is obtained prior to the end of the first 30 minute period.

>30 Minutes (and up to 96 hours) Post-Study Drug Initiation

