6.5.3. Transition and Termination Phase, Transition to Oral to Study Drug Termination

For transition to oral therapy, approximately 1 hour prior to the anticipated cessation of clevidipine infusion, the oral antihypertensive agent may be administered. At any time following administration of the oral antihypertensive agent, the clevidipine continuous IV infusion may be down-titrated or terminated in order to achieve the desired blood pressure level.

If treatment with an IV antihypertensive agent is still required after 96 hours of clevidipine therapy, the patient may be transitioned to an alternative IV antihypertensive agent according to the institutional standard of care.

If an additional/alternative IV antihypertensive agent is required, the clevidipine infusion may be down-titrated or terminated after initiation of the antihypertensive infusion in order to achieve the desired blood pressure level. An alternative/additional IV antihypertensive agent that is administered as 'rescue therapy' will be recorded as rescue therapy in the eCRF.

A PK sample will be taken just prior to discontinuation of study drug. Immediately before study drug termination, BP and HR will be measured, immediately followed by PK Sample 6, which will be taken from the indwelling arterial line within a 30 second window after BP and HR are obtained.

The following assessments will be performed during transition phase:

- BP and HR
 - at least every hour until study drug is terminated (up to 96 hours)
- PK Sample 5: only taken if transition to an additional antihypertensive is desired and concurrent administration at any time >30 minutes and up to 96 hours (taken in the order below)
 - BP and HR
 - PK Sample 5 (as applicable): taken immediately after BP and HR and before beginning administration of an additional antihypertensive agent
 - BP and HR, taken as instructed above

- PK Sample 6: obtain immediately prior to study drug termination (taken in the order below)
 - BP and HR
 - PK Sample 6, taken immediately after BP and HR
 - BP and HR to continue, as instructed above, every hour until study drug is terminated
- Serum chemistry (Section 6.3) every 24 hours (+ 1 hour) during study drug administration (up to 96 hours).
- Concomitant medications
- AE(s) and SAE(s)

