7.2.2. Concomitant Medication

The objective of monitoring concomitant medications to control BP is to determine the efficacy of clevidipine as monotherapy.

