10.3.2.2. Secondary Efficacy Endpoints

The secondary efficacy endpoints are:

• The percentage of patients who reach the initial prespecified target SBP range without falling below the lower limit of the prespecified target range during the first 30 minutes of clevidipine infusion

- The percentage of patients in whom the SBP falls below the lower limit of the pre specified target range at any time during the first 30 minutes and at any time during the entire study drug treatment period
- The percentage of patients in whom the SBP is within target range at each hour after the first 30 minute of clevidipine infusion
- The percentage of patients who require rescue therapy (i.e., receive any alternative IV antihypertensive drug) at any time during study drug treatment period or discontinuation due to adverse events.

The percentage of patients reaching each endpoint above will be calculated for overall and within each cohort using the number of ITT patients achieving the endpoint divided by the number of total ITT patients, and multiplied by 100.

Number and percent of patients achieving each endpoint during the first 30 minutes along with the calculated 95% confidence interval will be presented.

- Percent change in SBP from baseline at each time point during the 30 minutes of clevidipine infusion
- Percent change from baseline in SBP at each hour after the first 30 minutes of clevidipine infusion up to the cessation of infusion
- Percent change from baseline in SBP over the first 12 hours post study drug termination
- Percent change from baseline in heart rate during the first 30 minutes of clevidipine infusion and the rest of the treatment period

Percent change from baseline at each time point specified in above endpoints will be calculated for each ITT patient.

Descriptive statistics will be presented for overall and by cohort.

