Patients who receive alternative intravenous rescue therapy in addition to clevidipine may continue in the study. If transition from clevidipine to an oral antihypertensive agent is required, the clevidipine infusion may be down-titrated or terminated as appropriate to maintain the desired blood pressure. If the BP rises to an undesirable level upon cessation of clevidipine infusion, additional therapy may be administered or clevidipine infusion may be restarted (and continue until successful transition to an oral therapy has been achieved). Patients who receive prolonged clevidipine infusions and are not transitioned to other antihypertensive therapies should be monitored for the possibility of rebound hypertension for at least 8 hours after the infusion is stopped [Cleviprex Prescribing Information, 2011].

If treatment with an IV anti-hypertensive agent is still required after 96 hours of clevidipine therapy, the patient will be transitioned to an alternative IV antihypertensive agent according to the institutional standard of care.

The schedule of events/assessments is shown in Table 1 and the pharmacokinetic (PK) sampling time is shown in Table 2.

Table 1: Schedule of Events/Assessments

		Treatment Period		Follow-up Period  Post Study Drug Termination (up to 7 days after final dose)				
Study assessment	Screening Period 0 to -7 Days (prior to study drug initiation)	Treatment Phase 1 Initial Dosing 0 -1.5 minutes	Treatment Phase 2 Titration & Maintenance Phase >1.5 to 30 minutes & >30 minutes up to 96 hours	Treatment Phase 3 Transition & Termination Phase	Follow-up 1 Hour (+ 30 minutes	Follow-up 12 Hour (+ 30 minutes)	Follow-up 24 Hour (+ 30 minutes)	Follow-up 7- Day  (+ 1 day)
Informed consent	X 							
Medical history & Physical exam	X 							
Height & Weight	X 							
Prior Medications	X 							
BP (SBP, DBP) /HR	X2,3	X3	X 4,5	X 4,5	X e	X 6		
Pregnancy test	X2							
Hematology (Protocol Section 6.3)	X2							
Serum chemistry every 24 hours (Protocol Section 6.3)	X 		Х		X 			
SBP Target Range	X 		X 					
Enrollment via IVRS/IWRS	X 							
Study drug administration		X 	X 	X 				
PK sampling	X3,8	X3,8	X8	X8	X8			
Concomitant Medications		Х	Χ	Х	Х	Х	Х	
Oral Antihypertensive Administration				Х				
AE and SAE reporting	<del></del>			X12 —				$\rightarrow$

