# 10.2.5. Percent change in SBP from baseline at each time point during the 30 minutes of clevidipine infusion, at each hour after the first 30 minutes of clevidipine infusion up to the cessation of infusion, and over the first 12 hours post study drug termination

Blood pressure will be measured every 1.5 minutes for the first 30 minutes of infusion, every 10 minutes in the next hour, every 30 minutes for the next 2 hours then every hour until the study drug is terminated or maximum 96 hours from initiation of study drug is reached, whichever is earlier. Blood pressure will also be measured just prior to each PK blood draw and each dose adjustment, as well as every 1.5 minutes for 15 minutes after the dose adjustment. After termination of the clevidipine infusion, blood pressure will be taken every 15 minutes for the first hour, then every hour for a maximum of 12 hours.

Descriptive statistics on changes and percent changes from baseline in SBP will be summarized at each specified timepoint. A graph will be presented on percent change in SBP during the first 30 minutes after initiation of study medication by age cohort.

Individual patient graphs will present SBP across all timepoints along with the study drug dose levels in mg/h.

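### The hourly on-infusion blood pressure results count readings taken under IV rescue or an oral agent, with no rule separating them from control on clevidipine alone

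*SAP*

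**What the plan says.** SAP 10.2.3 sets the hourly endpoint: "The percentage of patients who stayed within target range at each hour after first 30 minutes of clevidipine infusion will be calculated". The count of patients in range is "divided by total number of patients in the analysis population, and multiplied by 100". For the SBP change, SAP 10.2.5 states: "Descriptive statistics on changes and percent changes from baseline in SBP will be summarized at each specified timepoint". Protocol 10.3.2.2 is equally general: "Percent change from baseline at each time point specified in above endpoints will be calculated for each ITT patient". None of these mentions a second antihypertensive.

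The treatment sections make such readings possible by design. Protocol 6.5.2 directs IV rescue when the maximum dose does not give the desired effect, and adds: "Patients who receive rescue therapy along with clevidipine may continue in the study". SAP 1.1 agrees: "Patients who receive alternative intravenous rescue therapy in addition to clevidipine may continue in the study". For the switch to oral therapy, Protocol 6.5.3 says that "approximately 1 hour prior to the anticipated cessation of clevidipine infusion, the oral antihypertensive agent may be administered".

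Two other places bear on the point. The primary time-to-target analysis (Protocol 10.3.2.1, SAP 10.1) censors a patient when another agent is given within the first 30 minutes. Protocol 7.2.2 states a purpose: "The objective of monitoring concomitant medications to control BP is to determine the efficacy of clevidipine as monotherapy".

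**The concern.** The hourly endpoints describe whether blood pressure stays controlled after the first 30 minutes, over an infusion that may last 96 hours. There is no comparator arm, so a reader will take the hourly percentage as what clevidipine achieved. Protocol 5.2.2 expects rescue only where study drug has not lowered blood pressure enough. For a rescued patient, a later in-range reading reflects at least partly the other drug, yet it is scored exactly like a reading on clevidipine alone.

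The plan recognises this problem in the first 30 minutes and handles it by censoring in the time-to-target analysis. It has no counterpart for the remaining hours. At stake is the meaning of two descriptive secondary endpoints. If the scoring is settled only after the data are seen, the more favourable version could be chosen.

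**Working it through.** **1. The plan's own figure.** The only design figure is the precision of the 30-minute attainment percentage (Protocol 10.1, SAP 16). With half-width = 1.96 × √(p(1−p)/n) and n = 80:

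- p = 0.90: 1.96 × √(0.90 × 0.10/80) = 0.0657, against the stated ±6.6%.
- p = 0.85: 1.96 × √(0.85 × 0.15/80) = 0.0782, against the stated ±7.8%.

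Both reproduce and neither is in dispute. The documents give no corresponding figure for the hourly endpoints.

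**2. Is there a rule elsewhere?** The candidates are:

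- The missing-data rule (Protocol 10.3, SAP 4) covers absent readings, not readings taken on a second drug.
- The windows in SAP 20.1.1 concern timing only.
- The censoring rule in SAP 10.1 applies to time-to-target in the first 30 minutes.
- SAP 10.2.4 gives one any-time percentage. It combines IV rescue with discontinuation for adverse events and leaves out oral agents.
- SAP 9 summarises concomitant medication without reference to hourly readings.
- The individual graphs in SAP 10.2.5 are specified with SBP and study drug dose only.

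None of them determines how an hourly reading on a second agent is scored. By default it counts.

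**3. Effect on the in-range percentage.** Let N be the analysis population, x the number in range at an hour, and k the number of those who are in range after the start of rescue. As written, the result is 100x/N. With rescued patients scored as not controlled on clevidipine it is 100(x−k)/N. The difference is 100k/N points, whatever x is.

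- N = 80: k = 4 (5%) gives 5 points; k = 8 (10%) gives 10 points.
- N = 20 (one cohort): each such patient is worth 5 points.

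**4. Illustration.** Assumptions, none from the documents: all 80 patients have a reading at the hour, 72 are in range, and about 90% of those on a second agent are in range (rounded to whole patients). Intervals are 95% Clopper–Pearson.

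| On second agent (in range) | As written | Scored as not controlled | Excluded from both counts |
|---|---|---|---|
| 4 (4) | 72/80 = 90.0% (81.2–95.6) | 68/80 = 85.0% (75.3–92.0) | 68/76 = 89.5% |
| 8 (7) | 72/80 = 90.0% (81.2–95.6) | 65/80 = 81.3% (71.0–89.1) | 65/72 = 90.3% |

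The result depends on the scoring rule. Treating these patients as failures moves it; excluding them hardly does.

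**5. Upper bound for 30-minute non-attainers.** The assumed 85–90% attainment leaves 80 × 0.10 = 8 to 80 × 0.15 = 12 patients. If every one were rescued, in range and still infusing at the hour, the shift would be 8/80 = 10 to 12/80 = 15 points. Rescue begun later, in patients who had attained target, is outside this bound.

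For the SBP change in SAP 10.2.5, the documents give neither the variability nor the effect of a second agent, so no size can be computed.

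**The case against.** The strongest reply is that the plan does determine a number. Every reading counts, which is a treatment-policy scoring and a legitimate choice. The endpoints are descriptive, no hypothesis is tested, and no error rate is affected. That stands, and it limits the weight of the point. But the choice is not declared, it differs from the handling in the time-to-target analysis, and a single-arm table of hourly control invites the reading that clevidipine produced it.

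Several stronger inferences are tempting, and the documents do not support them.

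- *That the hourly rule contradicts Protocol 7.2.2.* That section says why concomitant drugs are monitored. Monotherapy is called for only in the first 30 minutes, and later combined use is expressly allowed. The two sit badly together, but this is tension rather than contradiction.
- *That nothing else shows loss of control after 30 minutes.* SAP 10.2.4 reports IV rescue over the whole treatment period, and SAP 8, 10.2.2 and 14.2 add infusion rates, restarts, low readings and target changes. What is missing is the link to the hours.
- *That the hourly percentage must be too high.* The fixed denominator in SAP 10.2.3 appears to count patients whose infusion has ended as not in range, which pulls the other way. Clevidipine may also be stopped once the second agent starts, removing some rescued patients from on-infusion readings. Successful rescue hides failure; it does not make the result better than response without rescue.
- *That the last on-infusion hour carries an oral effect in every transitioned patient.* The oral agent may be given, clevidipine may be stopped at any time afterwards, and no onset time is stated.

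**Conclusion.** The point holds as a gap in scoring that should be closed. SAP 10.2.3 and the on-infusion part of SAP 10.2.5 use all hourly readings, including those with IV rescue or an oral antihypertensive on board. For rescued patients this credits the other drug's effect to clevidipine. The any-time rescue percentage reveals it only in part.

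The size is unknown because no rescue or oral-use rate is given. A shift of about 5–10 points rests on the assumption that 5–10% of the analysis population is on rescue and in range at the hour. A reader might take 10–15 points as the expected shift. It is an upper bound that equates every assumed 30-minute non-attainer with a successfully rescued patient still on infusion, and the documents do not support that equation. The shift is also specific to scoring rescue as not controlled.

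**What to change.** - **SAP 10.2.3:** show two lines at each hour: (a) all readings, as now; (b) patients counted as not within target on clevidipine alone from the start of IV rescue. Line (b) is confined to IV rescue because a planned oral transition is not in itself a failure of clevidipine.
- **SAP 10.2.5:** show the on-infusion hourly SBP change for all readings, and again for readings before any second agent given for blood pressure control. Define that as IV rescue or the oral transition agent, excluding drugs permitted for other purposes under Protocol 5.2.3.
- **Both tables:** footnote at each hour the number still on infusion and the number with a second agent on board.

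This changes analysis and presentation only. Rescue and concomitant medications are already recorded in the eCRF, and the existing censoring rule needs the time another agent is given. The sponsor should confirm that start times are also captured after 30 minutes. The cost is SAP wording, one extra line per table, and an hourly in-range percentage in line (b) that can only be equal to or less favourable than line (a).

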4.2. INCLUSION CRITERIA

Patients may be included in the study if they meet all of the following criteria:

- 1. Patient must be less than 18 years
- 2. Written informed consent obtained before initiation of any study-related procedures
- 3. The enrolling physician determines that patient will likely require a 15% reduction in BP during the perioperative course
- 4. Intra-arterial line available for blood pressure monitoring
- 5. Surgical procedure requiring at minimum 1 hour of anesthesia, in which IV antihypertensive therapy to control BP for at least 30 minutes is anticipated

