6.5.2. Dose Titration and Maintenance Phase, >1.5 minutes up to 96 hours

If the SBP range is not achieved within 1.5 minutes of the initial dose, the clevidipine IV infusion may be up-titrated (after PK Sample 2). At 1.5 minutes after this first dose titration, BP and HR will be measured, immediately followed by PK Sample 3, which will be taken from the indwelling arterial line within a 30 second window after BP and HR are obtained (ie, 1.5 min. - 2.0 min.). If the target SBP range is not achieved within 1.5 minutes of the first dose titration, the clevidipine IV infusion may be up-titrated (after PK Sample 3) per the proposed pediatric dosing schema, every 1.5 minutes (+ 30 second window where a PK sample is required). Dosing is at the discretion of the investigator and as tolerated by the patient, according to need, to achieve a SBP within the prespecified target range. Once the target range is achieved, BP and HR will be measured, immediately followed by PK Sample 4, taken from the indwelling arterial line within a 30 second window after BP and HR are obtained (ie, 1.5 min. - 2.0 min.).

The maximum clevidipine infusion rate of **CCI** cannot be exceeded. The clevidipine infusion rate may also be decreased as necessary at the discretion of the investigator to maintain SBP within the target range. If the target SBP range is achieved at any of the titration doses, that rate may be maintained for up to 96 hours to maintain the BP, or titrated up or down as necessary to maintain SBP within the target range.

After the initial 30 minutes, it may be necessary to alter the desired SBP target range over the course of the remaining treatment period. Any change in SBP target range must be recorded in the eCRF. It may also be necessary to adjust the dose titration up or down as needed at the discretion of the investigator to maintain SBP within the target range. BP and HR measurements are to be recorded according to the schedule below. Clevidipine infusion may be administered continuously for up to a maximum duration of 96 hours. Clevidipine may also be terminated at any time for safety reasons. If a dose adjustment is indicated, BP and HR should be recorded just prior to each study drug dose change as well as every 1.5 minutes for 15 minutes after the dose adjustment

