10.3. STATISTICAL ANALYSES

All study data will be summarized using descriptive statistics, graphs, and/or data listings. Descriptive statistics for continuous variables will include but not limited to number of patients (n), mean, standard deviation (SD), median, quartiles (Q1 and Q3), minimum (min) and maximum (max) values. Analysis of categorical variables will include frequency and percentage. Time to event variables will be analyzed using the Kaplan-Meier method.

No confirmatory hypothesis is established in this study; therefore no formal statistical hypothesis testing will be performed. However, p- values and/or two-tailed 95% confidence intervals may be generated to demonstrate the strength of the findings whenever appropriate.

Unless otherwise specified, missing data will not be imputed and will be excluded from the associated analysis.

Analyses will be presented for overall and by cohort.

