### 4. GENERAL STATISTICAL METHODOLOGY

All statistical analyses and summary information will be generated according to this statistical analysis plan (SAP). Any deviations from this SAP will be documented in the clinical study report (CSR).

Patient disposition, demographic and background characteristics will be presented for the safety, ITT and PK/PD populations. Unless otherwise specified, all efficacy analyses will be performed using the ITT population, all safety analyses will be performed using the safety population and all PK/PD analyses will be performed using the PK/PD population.

Continuous variables will be summarized using descriptive statistics including the number of patients reflected in the calculation (n), mean, standard deviation (SD), median, interquartile range (Q1 and Q3), minimum (min), and maximum (max). Frequencies and percentages will be displayed for categorical variables.

Because of the descriptive nature of this study, no formal statistical hypothesis testing will be performed. However, p-values and/or two-tailed 95% confidence intervals may be generated to demonstrate the strength of the findings whenever appropriate.

All data will be summarized for overall and by age cohort. Data listings will be provided for all data collected in the eCRF.

Unless otherwise specified for repeat pre-baseline assessments, the results from the final assessment made before or at the start of study medication will be used as baseline. If post-baseline assessments are repeated or unscheduled, the non-missing values from the first assessment will be used for generating summary statistics.

Unless otherwise specified (eg, in Section 8), missing data will not be imputed and will be excluded from the associated analysis.

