### 20. APPENDIX

#### 20.1. TIME WINDOWS

### 20.1.1. Visit windows for hemodynamic data (SBP, DBP and HR)

Hemodynamic data (SBP, DBP and HR) will be presented at every 1.5 minutes within 30 minutes of study drug infusion, at every 30 minutes for the next 3 hours, at every hour thereafter till the cessation of infusion and over 12 hours post study treatment. The time window is 30 seconds for 1.5 minutes presentation, 10 minutes for every 30 minutes presentation and 30 minutes for hourly presentation.

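### The hourly within-target percentage divides by all patients at every hour, so its ceiling falls as infusions end and it mixes BP control with treatment completion

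*SAP*

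**What the plan says.** **Denominator.** SAP 10.2.3 states that the hourly percentage "will be calculated using the number of patients who reached the endpoint divided by total number of patients in the analysis population", with a two-sided 95% CI at each hour. Protocol 10.3.2.2 covers this endpoint and three others with one sentence: "using the number of ITT patients achieving the endpoint divided by the number of total ITT patients". Under SAP 3.2, ITT membership needs dosing, a baseline SBP and one post-baseline SBP. It does not require being on infusion, or having a reading, at any given hour.

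**Infusion length.** Protocol 4.2 asks only that "IV antihypertensive therapy to control BP for at least 30 minutes is anticipated". Protocol 6.5.2 sets the other end: "Clevidipine infusion may be administered continuously for up to a maximum duration of 96 hours".

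**Which readings count.** SAP 10.2.3 does not say. Its companion endpoint in SAP 10.2.5 is limited to readings "at each hour after the first 30 minutes of clevidipine infusion up to the cessation of infusion"; the within-target endpoint carries no such limit. SAP 20.1.1 presents hemodynamic data "at every hour thereafter till the cessation of infusion and over 12 hours post study treatment", so it names the two periods separately. SBP is scheduled for 12 hours after termination (Protocol 6.5.4, SAP 10.2.5).

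**Missing data.** SAP Section 4 says that, unless otherwise specified, "missing data will not be imputed and will be excluded from the associated analysis". Protocol 10.3 has the same rule: "Unless otherwise specified, missing data will not be imputed and will be excluded from the associated analysis". Within SAP 10.2.3, the only provision for a missing assessment is to apply the Section 20.1.1 windows.

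**The concern.** The endpoint is meant to show whether SBP stays in range after the first 30 minutes. A fixed denominator suits the neighbouring endpoints in SAP 10.2.1, 10.2.2 and 10.2.4, which ask whether something happened over a period: every treated patient can be classified. It does not suit an endpoint evaluated afresh at each hour while patients finish treatment at different times. A patient who completed treatment successfully stays in the denominator but, once no reading counts for that hour, cannot enter the numerator.

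The hourly table could then suggest loss of control when treatment had merely ended, and the confidence interval would describe that mixed quantity. Two programmers could also both claim to follow the SAP, one applying the stated denominator and the other the missing-data exclusion, and produce different tables.

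**Working it through.** **1. The plan's own figure.** SAP Section 16 gives ±6.6% at 90% and ±7.8% at 85% for N = 80. From 1.96 × √(p(1−p)/80):
- p = 0.90: 1.96 × √(0.09/80) = 6.57 points
- p = 0.85: 1.96 × √(0.1275/80) = 7.82 points

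Both reproduce. They refer to reaching target within 30 minutes; the plan states no figure for the hourly endpoint.

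**2. Inputs.** N = 80 overall and 20 per cohort (Protocol 10.1). Two quantities are assumed because the documents do not give them: s, the share still infusing at a given hour, shown over a range; and c = 0.90, the share of infusing patients in range.

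**3. On-infusion readings only.** Literal percentage = c × s; percentage among those infusing = c; gap = c × (1 − s). Counts are rounded to whole patients, with exact (Clopper-Pearson) 95% CIs:

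| Still infusing | Literal rule | On-infusion denominator |
|---|---|---|
| 80 of 80 | 72/80 = 90.0% (81.2–95.6) | the same |
| 76 of 80 | 68/80 = 85.0% (75.3–92.0) | 68/76 = 89.5% (80.3–95.3) |
| 72 of 80 | 65/80 = 81.3% (71.0–89.1) | 65/72 = 90.3% (81.0–96.0) |
| 60 of 80 | 54/80 = 67.5% (56.1–77.6) | 54/60 = 90.0% (79.5–96.2) |
| 40 of 80 | 36/80 = 45.0% (33.8–56.5) | 36/40 = 90.0% (76.3–97.2) |
| 20 of 80 | 18/80 = 22.5% (13.9–33.2) | 18/20 = 90.0% (68.3–98.8) |
| 10 of 20 (one cohort) | 9/20 = 45.0% (23.1–68.5) | 9/10 = 90.0% (55.5–99.7) |

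Even with every infusing patient in range (c = 1), the literal figure cannot exceed s: with 40 of 80 infusing it is 50%.

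**4. Post-infusion readings also count.** Let q be the share of finished patients in range, all of them within 12 hours of termination. With half infusing, the percentage is 0.5 × 0.90 + 0.5 × q:
- q = 0: 45%
- q = 0.50: 70%
- q = 0.90: 90%

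The gap may therefore vanish or be as large as in step 3. It does not vanish at later hours. A patient infused for 1 hour has no scheduled SBP after about hour 13, yet stays in the denominator at any later hour reported, up to hour 96. The ceiling is then the share infusing or within 12 hours of termination.

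**5. Scale.** On the step 3 reading, the expected gap passes 6.6 points once 6 of 80 infusions have ended (0.9 × 6/80 = 6.75 points; with 5 ended, 5.6). For a cohort of 20 the matching half-width is 1.96 × √(0.09/20) = 13.1 points, passed once 3 have ended (0.9 × 3/20 = 13.5; with 2 ended, 9.0). This only sets the gap beside sampling error. The ±6.6 is precision for the primary endpoint, not a tolerance for this one.

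**The case against.** **The missing-data rule already settles it.** Both documents exclude missing data, the SAP's named example of an exception is Section 8 rather than 10.2.3, and the denominator sentence is boilerplate. On a purposive reading, a patient whose infusion has ended has no later hourly timepoint in either numerator or denominator. This is a reasonable guess at intent and a real limit on the point. But the rule yields wherever something else is specified, and 10.2.3 does specify a denominator. A reading after infusion end may also be not applicable rather than missing. The 20.1.1 windows only select a nearby reading. The SAP restricts denominators when it means to: SAP 11.2.2 limits laboratory rates to patients with a suitable baseline and a post-baseline value.

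**On-infusion-only is an inference.** This stands. The reference to clevidipine infusion in the endpoint's title may qualify only the first 30 minutes, and the cessation limit of the companion endpoint is absent. A reader might infer that a finished patient can never count as in range; the documents do not establish that for the 12 hours after termination. A reader might also infer that the percentage must fall whatever the BP control. Only the ceiling must fall: the observed figure can rise between two hours if control improves among those assessed.

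**An all-ITT percentage is legitimate.** With on-infusion readings only, it is the share of treated patients on drug and in range. It is worth keeping under that label, but it does not by itself show whether SBP stays in range.

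**The consequence is small.** Largely true. The study is descriptive, with no formal hypothesis testing. The n behind the hourly SBP changes, the individual SBP-with-dose graphs, the exposure summaries and the listings would let a reader partly reconstruct the on-infusion rate.

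**Conclusion.** The point holds, at minor to moderate severity. Followed as written, SAP 10.2.3 and Protocol 10.3.2.2 give an hourly percentage capped at the share of patients still assessable, under either reading of which SBP values count. The general missing-data rule points the other way without clearly overriding the stated denominator.

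The size is not known. It rests on an assumed share infusing and an assumed 90% in range. With half of 80 infusing, it runs from no gap to 45 points, depending on whether post-infusion readings count and how many are in range. It is small at hours when few infusions have ended.

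A reader might take this as undermining the trial's main results. The documents do not support that: the primary endpoints concern the first 30 minutes, and the end-of-cohort precision check in SAP Section 15 uses that same event. Neither they nor the sample size is affected. The defect is confined to one descriptive secondary endpoint.

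**What to change.** In SAP 10.2.3, with a matching sentence in Protocol 10.3.2.2:

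1. State that only readings taken during clevidipine infusion count.
2. Set the denominator at each hour to ITT patients on clevidipine at that hour, using the on-drug segments of SAP Section 8 so that restarts are included, with an SBP reading in the Section 20.1.1 window.
3. Report n at each hour beside the percentage and its CI.
4. Keep the all-ITT percentage as a labelled supplement, with the termination reasons already planned in SAP Section 8 beside it.

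**Cost.** A few sentences in the SAP and one in the protocol. No new data are needed, because on-drug segments and termination reasons are already used for the exposure summaries.

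**Downsides.** Late-hour intervals widen (68.3 to 98.8 on n = 20 in the example above). The on-infusion set is also selected: patients stopped for adverse events or moved to other therapy leave the denominator, which can bias the control rate upward. Item 4 discloses that selection but does not remove it.
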